10.5.3 Collection of pregnancy information

Pregnancy information will only be collected after obtaining written informed consent from the pregnant female trial subject (or if a male trial subject's partner becomes pregnant, written informed consent from both).

The initial and follow-up information must be documented on the paper-based Pregnancy Reporting Form and submitted to the sponsor within 24 h of learning of a trial subject's pregnancy/partner's pregnancy and in the CRF. The completed form needs to be sent to the Safety Report Fax number or E-Mail given in Section 10.4.4. Completed pregnancy forms must be signed by an investigator before faxing/mailing them to the sponsor. Blank reporting forms are provided to the investigator during the site initiation visit and are filed in the ISF.

Clinical Trial Protocol Trial number: BNT165-01 Page 77 of 82 Version: 4.0 Date: 13 FEB 2023

The investigator will collect follow-up information on the trial subject/trial subject's partner and the neonate, and the information will be forwarded to the sponsor. Pregnancy follow-up should describe the outcome of the pregnancy, including any voluntary or spontaneous termination, details of the birth, the presence or absence of any congenital abnormalities, birth defects, maternal or newborn complications and their presumed relation to the IMP. Generally, the follow-up will be of a duration determined in consultation with the pediatrician.

While pregnancy itself is not considered to be an AE or SAE, any pregnancy complication (spontaneous abortion, bleeding, preeclampsia, etc.) or elective termination of a pregnancy will be reported as an AE or SAE.

A spontaneous abortion is always considered to be an SAE and will be reported as such. Any post-trial pregnancy-related SAE considered reasonably related to the trial treatment by the investigator will be reported to the sponsor. While the investigator is not obligated to actively seek this information in former trial subjects, the investigator may learn of an SAE through spontaneous reporting.

10.6 Liver safety: Suggested actions and follow-up assessments Not applicable.

10.7 Standard definitions

10.7.1 Trial site start/closure and trial discontinuation

The date of first site open (first act of recruitment of potential trial subjects for this trial) is the "trial start date".

The date when all trial sites are closed is the "date of trial closure".

A trial site is considered closed when all required documents and trial supplies have been collected and a trial site closure visit has been performed.

All trial sites will be closed upon trial completion.

The investigator may initiate trial site closure at any time, provided there is reasonable cause and sufficient notice is given in advance of the intended trial site closure.

The sponsor reserves the right to close a trial site early or to terminate the whole trial or to suspend the whole trial (a temporary halt; an unplanned interruption of the conduct of a trial by the sponsor with the intention to resume it) at any time for any reason.

Reasons for the sponsor to close a trial site early may include but are not limited to:

- Failure of the investigator to comply with the protocol, the requirements of the IRB/IEC or local health authorities, the sponsor's procedures, or GCP guidelines
- Inadequate recruitment of trial subjects by the investigator

Reasons for the sponsor to suspend the whole trial may include but are not limited to:

• When there are safety concerns (e.g., if there is an IRC recommendation)

Page 78 of 82 Version: 4.0 Date: 13 FEB 2023

Reasons for the sponsor to prematurely terminate the whole trial may include but are not limited to:

- When there are safety concerns (e.g., if there is an IRC recommendation)
- Discontinuation of further trial treatment development

If the trial is prematurely terminated or suspended, the sponsor shall promptly inform the investigators, the IECs/IRBs, the regulatory authorities, and any CROs used in the trial of the reason, as specified by the applicable regulatory requirements. The investigator shall promptly inform the trial subjects and should assure appropriate follow-up.

10.7.2 Trial completer and end of trial definitions

A trial subject is considered to have completed the trial if they have completed the last scheduled procedure shown in the SoA (see Section 1.3).

The end of the trial is defined as the date of last scheduled procedure (final date on which data were or are expected to be collected) as shown in the SoA for the last trial subject in the trial globally.

For definitions of the trial and site start/closure, see Section 10.7.1.

10.8 Protocol amendments and updates

10.8.1 Update to protocol version 2.0

This amendment implements changes in the primary endpoint and pausing rules.

This update will be issued before the planned trial subjects will be enrolled into the trial.

A comparison of every new sponsor approved protocol version with the next approved version is filed together with the protocol in the TMF.

Detailed description of changes

Minor editorial changes, such as rewording or improvement of language for consistency, are not specifically listed.

See the table for a summary of the reasons for changes compared to the previous version:

Section	Reason for change
Section 1.1 Trial synopsis (Objectives), Section 3 Objectives and endpoints	Clarification on primary endpoint i.e., AEs will be collected continuously until 28 d after each dose and not up to 28 d post-Dose 3.
Section 7.1 Discontinuation or pausing (temporary halting) of trial treatment	Clarification on the reporting of AEs contributing to pausing rules i.e., Grade 3 AEs or above possibly related, contributing to pausing rules will be collected on an expedited timeline (within 24 h) like that of an SAE.
Section 10.4.4 Reporting of SAEs	Sponsor's email ID has been updated to PPD

Page 79 of 82 Version: 4.0 Date: 13 FEB 2023

10.8.2 Update to protocol version 3.0

This amendment implements changes in the pausing rules requested by the FDA.

This update will be issued before the planned trial subjects will be enrolled into the trial.

A comparison of every new sponsor approved protocol version with the next approved version is filed together with the protocol in the TMF.

Detailed description of changes

Minor editorial changes, such as rewording or improvement of language for consistency, are not specifically listed.

See the table for a summary of the reasons for changes compared to the previous version:

Section	Reason for change
7.1.1 Cohort trial treatment pausing rules	Changes in the pausing rules requested by the FDA.

10.8.3 Update to protocol version 4.0

This amendment implements changes in the primary and exploratory endpoints, SoA, trial treatment, exclusion criteria and treatment for specific adverse reactions requested by FDA, also includes update of the sponsor's new e-mail and fax number and sponsor's contact e-mail address. Other changes were clarifications (see the below tabular summary).

These changes have no impact on the planned trial objectives or trial conduct.

A comparison of every new sponsor approved protocol version with the next approved version is filed together with the protocol in the TMF.

Detailed description of changes

Minor editorial changes, such as rewording or improvement of language for consistency, are not specifically listed.

See the table for a summary of the reasons for changes compared to the previous version:

Section	Reason for change		
1.1, 1.3, 3 and 8.3.1	Change in the MAAEs collection time		
1.1, 3 and 8.8	Clarification on exploratory endpoints		
1.1 and 6.1	Addition of isotonic NaCl solution (0.9%) as matching placebo in all instances as requested by FDA.		
1.3	Removal of urine dipstick analysis and microscopic urinalysis, changes in blood volume and clarification on ECG timings		
1.3	Change in non-leading wellbeing calls timings		
1.3, 4.2 and 8.2.10	Addition of wellbeing calls at 14 (+1) d after each IMP dose and to solicit local injection site reactions starting after 7 d and through 14 d post-IMP administration as requested by FDA.		

Page 80 of 82 Version: 4.0 Date: 13 FEB 2023

Section	Reason for change
5.2	Addition of exclusion criteria #19."Current febrile illness (body temperature ≥38.0°C/≥100.4°F) or febrile illness within 48 h of Visit 0" as requested by FDA.
8.5	Addition of two subsections 8.5.1 and 8.5.2. Section 8.5.1 includes guidance for investigators on myopericarditis as requested by FDA.
10.4.4	Addition of new sponsor e-mail and fax number, sponsor contact e-mail address valid as of 01 MAR 2023

12 TOXICITY MANAGEMENT/MITIGATION PLANS

12.1 Toxicity management/mitigation plans for local and systemic reactogenicity

Based on experience with other BioNTech RNA-based vaccines and published data from other RNA-based vaccines, it is anticipated that subjects may experience local and systemic (flu-like) reactogenicity events of mostly mild to moderate severity following the administration of RNA vaccines within 1 to 3 d. Symptomology may include injection site pain, fever, chills, rigors, tachycardia, arthralgia, myalgia, lymphadenopathy, headache or nausea.

Treatment of these events is at the discretion of the investigators; however, the following management suggestions are provided:

- After the first occurrence of flu-like symptomatology, subjects can be treated with standard therapeutic dose of acetaminophen (preferable) rather than NSAIDs, according to local guidance after the immunization.
- Corticosteroids should be avoided as either prophylaxis or treatment as it counteracts the effects of immunization.
- Self-limited Grade 3 reactogenicity events may not require discontinuation of future trial injections, and the local investigator may discuss with the trial Medical Monitor.
- Grade 4 reactogenicity events will lead to discontinuation of future injections in the trial subject.

If subjects experience progression of flu-like symptomatology or non-resolution of the symptoms later than 7 d post-immunization, the trial Medical Monitor should be informed.

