7.1.1 Cohort trial treatment pausing rules

Grading scales for the intensity of AEs and SAE will be based on guidance from the US Food and Drug Administration "Toxicity Grading Scale for Healthy Adult and Adolescent Volunteers Enrolled in Preventive Vaccine Clinical Trials".

If any of the below is met in a given cohort and after any dose, no additional trial subjects will be assigned to the cohort and administration of trial treatment, including administration of Dose 2 and/or Dose 3 for affected cohorts and any higher DL(s), will be paused until the IRC reviews the event(s):

- Any SAE developed by subject administered with trial treatment (at any DL), for which there is no alternative, plausible, attributable cause and which is assessed by the investigator, or the sponsor as possibly related.
- Any severe (Grade 3) hypersensitivity or any anaphylactic AE that occurs within 7 d
 of vaccination without a clear alternative cause.

NOTE: Grade 3 hypersensitivity is defined as symptomatic bronchospasm with or without urticaria, parenteral intervention, allergy related edema/angioedema, or hypotension. Grade 4 hyposensitivity encompasses all life-threatening events and for which urgent intervention is indicated.

Clinical Trial Protocol Trial number: BNT165-01 Page 40 of 82 Version: 4.0

Date: 13 FEB 2023

- Any Grade 4 AE after administration of trial treatment (at any DL) that is assessed as possibly related by the investigator, or for which there is no alternative, plausible, attributable cause.
- Any case of immune-related AE, including but not limited to myocarditis, pericarditis or myopericarditis, that is assessed as possibly related by the investigator, or for which there is no alternative, plausible, attributable cause.
- Any case of fever >40.0°C (measured orally) persisting for over 6 h despite the use of antipyretics after administration of trial treatment (at any DL) that is assessed as possibly related by the investigator and/or sponsor, or for which there is no alternative, plausible, attributable cause.
- If two trial subjects develop the same or similar Grade 3 or higher AE at least possibly related to trial treatment (solicited injection site reactions, solicited systemic reactions, unsolicited AEs, and laboratory abnormalities considered at least possibly related to trial treatment).

NOTE:

- Reactogenicity e-diary data confirmed by the investigator as being entered by the subject in error will not contribute toward a pausing rule.

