7.1.3 Permanent discontinuation of trial treatment

Trial treatment administration will be permanently discontinued for an individual trial subject if any of the below criteria are met.

- Any Grade 4 reactogenicity event considered to be possibly related
- Pregnancy
- Any severe acute systemic hypersensitivity AE or anaphylactic reaction of Grade 3 or above assessed as possibly related to IMP
- Any suspected or confirmed immune-related AE, including but not limited to myocarditis or pericarditis assessed as possibly related to IMP

Clinical Trial Protocol Trial number: BNT165-01 Page 41 of 82 Version: 4.0 Date: 13 FEB 2023

After pausing trial treatment according to Sections 7.1.1 and 7.1.2, the IRC may recommend a permanent discontinuation of trial treatment overall, in a cohort, or for a single trial subject.

A permanent discontinuation of trial treatment may also occur for non-medical reasons at the judgment of the investigator or the subject (i.e., subject moves to a new location).

Trial subjects permanently discontinued from trial treatment will complete all assessments planned for the actual week or day of that visit as listed in the SoA (Section 1.3), at minimum, all assessments scheduled at Visit 14 should be performed. The only exception is pregnant women who will not have further blood draws, but will otherwise complete planned assessments, if required including pregnancy follow-up until birth.

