- Record the worst grade for each symptom in the e-diary at approximately the same time every evening on the day of IMP injection and then every day in the evening for a total of seven consecutive days.
- Measure their body temperature using the provided device and record their body temperature in the e-diary every day including the day of IMP injection.
- To assess any solicited local reactions at the injection site as described in Section 8.2.6.1 and solicited systemic reactions as described in Section 8.2.6.2.
- To contact the site immediately in case of severe or potentially life-threatening reactogenicity events.

Clinical Trial Protocol Trial number: BNT165-01 Page 47 of 82 Version: 4.0 Date: 13 FEB 2023

Investigators will review subject-reported e-diary data at the times given in the SoA (Section 1.3).

Only an investigator or medically qualified person is able to confirm Grade 3 or a potentially life-threatening Grade 4 event for recording in the EDC system.

If a trial subject experiences confirmed Grade 4 reactogenicity, the investigator must immediately notify the sponsor and, if it is determined to be related to the administration of IMP, further IMP administration will be discontinued in that trial subject (see Section 7.1).

If a trial subject experiences a potential Grade 3 reactogenicity or higher, the subject must immediately notify the investigator or some other medically qualified person, who will then confirm the grading, the confirmed Grade 4 reactogenicity will be recorded by the investigator as an SAE. Data for solicited Grade 3 or lower events do not need to be reported separately by the investigator as AEs in the EDC system, unless they are reported as an unsolicited event or extends beyond the 7 d.

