It is sufficient to document the causality in the source data and CRF as:

- Related (= there is a reasonable possibility of a causal relationship) or
- Not related (= there is no reasonable possibility of a causal relationship)

The relationship or association of an AE or SAE to a trial treatment/trial procedure will be assessed by the investigator after having evaluated all accessible data and, if necessary, he/she will re-evaluate the case as new information becomes available.

Events caused by the procedure of trial treatment administration should be differentiated from events caused by the trial treatment itself. Only events suspected to be caused by the IMPs itself should be documented as suspected adverse reactions but not events caused by the procedure of trial treatment administration.

In this trial, it cannot be excluded that during the course of the trial some procedures give rise to AEs which are related to the trial procedure and not to the trial treatment. Procedure-related AEs can occur on the site of injection of the trial treatment (e.g., redness, swelling, hematoma or itching) or during or after trial-specific procedure (e.g., discomfort after blood drawing). These events must be reported in the CRF on Adverse Event pages as "related to trial procedure" with the causing procedure specified.

Notes applicable for relationship to trial procedures including trial treatments

There may be situations in which an SAE has occurred, and the investigator has minimal information to include in the initial report to the sponsor. However, it is very important that the investigator always makes an assessment of causality for every event before the initial transmission of the SAE data to the sponsor.

The investigator may change their opinion of causality in light of follow-up information and send a SAE follow-up report with the updated causality assessment.

The causality assessment is one of the criteria used when determining regulatory reporting requirements.

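### Protocol Section 12.1 stops injections after any Grade 4 reactogenicity event, while Sections 7.1.3 and 8.2.7 make stopping depend on relatedness

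*Protocol*

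**What the plan says.** Three places in the current protocol say when a Grade 4 reaction ends dosing for an individual subject.

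- **Section 12.1** (toxicity management): "Grade 4 reactogenicity events will lead to discontinuation of future injections in the trial subject". No causality condition is attached. The list containing this bullet is introduced by "Treatment of these events is at the discretion of the investigators; however, the following management suggestions are provided".
- **Section 7.1.3** (permanent discontinuation) lists, among the criteria that end treatment for a subject, "Any Grade 4 reactogenicity event considered to be possibly related".
- **Section 8.2.7** (site and investigator tasks for the e-diary) has the investigator notify the sponsor at once of a confirmed Grade 4 reaction and then adds "if it is determined to be related to the administration of IMP, further IMP administration will be discontinued in that trial subject", with a pointer to Section 7.1.

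Causality is recorded under Section 10.4.3 on two levels. Related means that a causal link is a reasonable possibility. The other level is defined as "Not related (= there is no reasonable possibility of a causal relationship". Possibly related is not a level on this scale.

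**The concern.** Section 12.1 asks only whether the reaction was Grade 4. Sections 7.1.3 and 8.2.7 also ask whether it was related. A site that follows 12.1 and a site that follows 7.1.3 could each comply with the protocol and yet reach different decisions about the same event.

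The disputed event can occur. Reactogenicity is captured by what is solicited and when, that is, listed symptoms over 7 days after each dose, not by a judgement of cause. In the systemic grading table an oral temperature above 40.0°C is Grade 4 whatever its origin, so an intercurrent infection in the diary week could qualify. The conditional clause in 8.2.7 would have no purpose if every Grade 4 reaction counted as related.

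At stake is whether a healthy volunteer in a first-in-human trial receives the remaining doses. What is reported for those later doses follows from that.

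**Working it through.** The protocol states no figure for this rule, so the main check is a comparison of the texts.

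**Step 1: apply each section to each causality judgement**

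| Grade 4 solicited reaction judged | Section 12.1 | Section 7.1.3 | Section 8.2.7 |
|---|---|---|---|
| Related | Stops | Stops | Stops |
| Possibly related | Stops | Stops | Stops if determined to be related includes possibly related |
| Not related | Stops | Criterion not met | Criterion not met |

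The first row shows agreement. The third is a plain inconsistency between 12.1 and the other two sections. The second depends on how 8.2.7 is read.

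**Step 2: resolve the second row as far as the text allows.** On the Section 10.4.3 scale, an event with a reasonable possibility of a causal link is recorded as related. An event called possibly related would therefore normally fall on the related side. Section 8.2.7 also refers to Section 7.1, which contains 7.1.3. The two wordings probably set one threshold, but no sentence in the protocol equates them.

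**Step 3: see whether another rule settles the third row.** The cohort pausing rule in Section 7.1.1 covers "Any Grade 4 AE after administration of trial treatment (at any DL) that is assessed as possibly related by the investigator" and, as an alternative, Grade 4 events with no other plausible cause. A Grade 4 reaction judged not related, with another plausible cause, meets neither limb. That rule therefore does not bring the case to the IRC automatically.

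**Step 4: size.** Inputs:
- 16 vaccine recipients per cohort (Protocol 4.1.1).
- Local and systemic reaction summaries use the Safety Set, less subjects with no e-diary data over the 7 days after vaccination (SAP 8.5.2.1 and 8.5.3).
- Percentages for event data such as AEs use all subjects in the analysis set (SAP 8.1).

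If one vaccine recipient is stopped, that subject has no diary data for the doses not given. Applying the exclusion dose by dose:

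- share of the cohort's vaccinees affected = 1/16 = 6.25%;
- denominator for each missed dose = 16 − 1 = 15, so each remaining subject counts 1/15 = 6.67% instead of 6.25%.

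Stopping after Dose 1 affects the summaries for Doses 2 and 3. Stopping after Dose 2 affects Dose 3 only. An event after Dose 3 changes nothing here.

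The AE, MAAE and SAE denominators stay the same, because one dose is enough for membership of the Safety Set. The counts that do change are treatment discontinuations with their reasons (SAP 8.2) and the reasons for not receiving Dose 2 or 3 (SAP 8.5.1).

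**The case against.** The best defence is that the protocol shows where discontinuation criteria belong. Sections 1.1 and 6.6 send the reader to Section 7 for them, and SAP 3.2 points to protocol Section 7.1. Section 12.1 offers its bullets as suggestions and describes reactions that follow RNA vaccination, so it may have vaccine-attributed reactions in mind already. Sites do not act alone either: a confirmed Grade 4 reaction goes to the sponsor immediately and is recorded as an SAE whatever its cause, and Section 7 asks that safety concerns be discussed with the sponsor to decide on continuation.

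Much of this stands, and it limits the point. It does not remove it. The Grade 4 bullet is worded as a consequence that will follow, whereas the Grade 3 bullet just above it is permissive, so the section itself separates the two. Section 2.3.3 names 12.1 as the guidance for risks of BNT165b1 administration, so sites are directed there too. No sentence says that Section 7 prevails.

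Four stronger readings are tempting, and the documents do not support them:

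- **Three different thresholds.** A reader might infer this from the three wordings. The scale in 10.4.3 and the pointer in 8.2.7 suggest two at most.
- **Opposite instructions.** Section 7.1.3 lists when treatment must end. It does not tell a site to continue after an unrelated Grade 4 event. Section 7.1.2 allows an individual pause for any safety concern, pending IRC review, and the IRC may then recommend stopping for that subject.
- **Loss of comparability between sites.** Summaries are by dose level with pooled placebo, and no subgroup analysis or hypothesis test is planned. No planned analysis compares sites.
- **An effect on every later-dose percentage.** The 6.25% concerns the solicited-reaction summaries only.

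**Conclusion.** The inconsistency is real but narrow. Section 12.1 carries no causality condition, Sections 7.1.3 and 8.2.7 do, and the sections differ for a Grade 4 solicited reaction judged not related. A second, smaller gap is that possibly related and determined to be related are never tied to the scale in 10.4.3, although they probably mean the same.

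The effect is on one subject at a time: whether the remaining doses are given, how the discontinuation is counted, and one of 16 vaccinees in the later-dose solicited-reaction denominators. No sample-size figure changes. It is worth correcting because it bears on subject safety, not because it threatens the analysis.

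This rests on two assumptions. The first is that such events are rare. The documents give no rate for Grade 4 reactions, but Sections 4.2 and 12.1 describe reactions as usually or mostly mild to moderate. The second is that the e-diary exclusion is applied separately for each dose. If a subject with diary data after any dose were kept throughout, the solicited-reaction denominators would not change, and only the dosing decision and the discontinuation counts would be affected.

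**What to change.** Sections 7.1.3, 8.2.7 and 12.1 must be reconciled to one condition for ending injections after a Grade 4 reaction. The clinical team chooses the condition; this review does not say which is right.

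State the condition once and have the other two sections refer to it. Express any reference to relatedness in the terms of the Section 10.4.3 scale, so that it is clear how possibly related maps onto related and not related.

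The cost is protocol wording only. Sample size, schedule and planned SAP tables need no change.
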